## SCHEMATIC OF STUDY DESIGN

FIGURE 1: Study flow.

AS, aortic stenosis; AVR, aortic valve replacement (by surgery or transcatheter aortic valve implantation); TAVR, Transcutaneous aortic valve replacement; TTE, trans-thoracic echocardiography; IC, informed consent; SPECT, Single-photon emission computed tomography; FFR, fractional flow reserve; RFR, resting full cycle ratio; IMR, index of microcirculatory resistance; LV, left ventricle.

FIGURE 2: Secondary Objective.

FFR, fractional flow reserve; RFR, resting full cycle ratio; IMR, index of microcirculatory resistance; iFR, instantaneous wave-free ratio; SPECT, Single-photon emission computed tomography; AS, aortic stenosis; MVD, microvascular/microcirculatory dysfunction. Yamanaka *et al.* compared FFR versus iFR with SPECT as the standard for ischemia.

## SYSTEMATIC PROTOCOL STUDY SYNOPSIS

Title	Coronary and Microcirculatory measurements in patients with Aortic valve Stenosis, the COMIC AS study.
Design	A single centre, prospective, cohort study assessing the changes in intracoronary flow and pressure before and 6 months after aortic valve intervention.
Objectives	
Primary endpoint:
 
 
1. Aortic valve intervention results in a significant change in fractional flow reserve (FFR) 6 months after SAVR/TAVI.
 
 
Secondary endpoints:
 
 
2. Measurement of IMR in patients with AS prior to intervention and 6 months after TAVI/SAVR.
 
3. Corrected FFR (based on baseline IMR) correlates with the post-intervention FFR.
 
4. IMR at baseline improves the ischemia prediction of FFR (compared with SPECT).
 
5. Comparison of the diagnostic performance of FFR and RFR with SPECT ischemia.
 

Treatment	There is no study-related intervention. Aortic valve intervention is carried out according to normal clinical practice.
Follow-up	Patients will undergo clinical assessment, TTE and cardiac catheterization 6 months after aortic valve intervention.
Inclusion criteria	
 
1. Patient undergoing the procedure is older than 18 years, has severe aortic valve stenosis (according to ESC guidelines) and is planned for cardiac catheterization as part of the pre-operative (SAVR) or pre-percutaneous (TAVI) work up.
 

	
2. The patient has an intermediate (50-90%) coronary lesion that requires further evaluation.
 
3. The patient undergoing the procedure is male, or if female, has no childbearing potential or is not pregnant.

Exclusion criteria	
1. The procedure is an emergency and/or the patient is unstable.
 
2. Pregnancy or lactation
 
3. Haemodynamically unstable patients
 
4. Killip class III-IV heart failure
 
5. Previous coronary artery by-pass in the artery being assessed
 
6. Contra-indications for adenosine administration: severe asthma or pre-existing type 2 AV-block
 
7. No significant coronary artery disease (<50% stenosis on angiography).
 
8. Critical coronary artery disease deemed by the Heart Team to require immediate revascularization
 
9. Patients will be excluded from the SPECT study (secondary objective) if they have a left main coronary stenosis >50%, triple vessel disease, previous myocardial infarction in the same coronary artery & tandem lesions (separated by >10mm) requiring independent evaluation in the same coronary artery since these factors interfere with the SPECT analysis.

Number of patients	
 
• 80 patients with pre- and post-intervention (TAVI or SAVR) catheterizations 
 
○ Fifty Eight t (58) patients with pre- and post-interventions catheterizations will be sufficient to detect a reduction in the FFR from 0.82 to 0.79 with an alpha level of 0.05 and power of 0.80. A total sample of 100 with baseline measurements and subsequent 80 patients who will undergo (T)AVR without revascularisation and are eligible for a pre-and post-
 
 
 

	
intervention catheterization will allow for a 25% drop-out during the follow up phase of the study.
 
 
○ This flow with patient numbers and dropout is illustrated in figure 1 for clarity.
 

Study duration	3 years (or earlier when the 80 pt's with an aortic valve procedure without revascularisation will be included)

## 1. BACKGROUND

Aortic stenosis (AS) is the most common primary valve disease leading to surgery or catheter intervention in Europe, with a growing prevalence due to the aging population. Severe aortic valve stenosis, defined by a mean gradient over the aortic valve of greater than 40mmHg or an aortic valve area of less than 1.0cm^2, is associated with significant morbidity and mortality and is treated by surgical valve replacement (SAVR) or transcatheter aortic valve implantation (TAVI). However, significant coronary artery disease (CAD) is reported in more than 60% of patients with AS, and needs to be correctly assessed because untreated significant CAD is associated with adverse outcomes.

Current guidelines recommend intra-coronary pressure measurement using either fractional flow reserve (FFR) or non-hyperemic pressure ratios (NHPRs) for the assessment of intermediate coronary artery lesions before revascularization. A FFR of  $\leq 0.80$  or a NHPR of  $\leq 0.89$  is considered to indicate that a coronary lesion is significant. Non-hyperemic pressure ratios include the instantaneous wave-free ratio (iFR) and the resting full cycle ratio (RFR), which have been shown to be comparable. However, correctly identifying hemodynamically significant coronary stenoses is difficult in patients with AS because of the hypertrophic remodelling related to the valve pathology. Aortic stenosis is associated with a significant increase in left ventricular (LV) mass resulting in pathological changes in coronary and LV hemodynamics, which are associated with coronary microvascular dysfunction.

With the development of microvascular dysfunction, intra-coronary pressure measurements become less reliable and, currently, whether FFR, or the NHPRs, can reliably detect myocardial ischemia in patients with severe AS is controversial, making it difficult for physicians to correctly determine whether or not coronary lesions should be revascularized prior to TAVI or at the time of SAVR. Yamanaka *et al.* recently reported a strong correlation of iFR with FFR in patients with

AS and intermediate CAD. They determined that the optimal iFR threshold for detecting ischemia compared with  $^{99m}\text{Tc}$  single-photon emission computed tomographic (SPECT) myocardial perfusion imaging was 0.82, while the cut-off for FFR was 0.83. This is in contrast to the large, outcome-based randomized controlled studies in patients without AS, and different to the current guideline cut-offs of  $\leq 0.89$  for resting indices and  $\leq 0.80$  for FFR. The RFR threshold for detecting ischemia has not yet been determined in patients with AS.

A more comprehensive study with performance of intra-coronary measurements before and after TAVI may help determine the effect of adverse LV remodelling and microvascular dysfunction on the hemodynamic measurement of coronary artery lesions in patients with severe AS. However, the timing of the follow-up measurements has not been clearly defined. Several studies have performed acute measurements pre- and post-TAVI but no invasive study (measuring FFR and/or resting indices) has been performed after allowing adequate time for reverse remodelling in order to really determine the effect of microvascular reverse remodelling on intra-coronary hemodynamic measurements. Exactly how long is needed after TAVI to ensure adequate myocardial and microvascular remodelling has occurred in order to appropriately use intra-coronary hemodynamic measurements is not known at this stage. One MRI-based study demonstrated a significant reduction in indexed LV mass from  $76\text{g}/\text{m}^2$  to  $68\text{g}/\text{m}^2$  within a few days. In another study, echocardiographic ejection fraction and LV global longitudinal strain improved significantly when measured 10 days after TAVI. However, indexed LV mass improvement was only significant during long-term (months-to-years) follow up. In a more recent, echocardiographic-based study, indexed LV mass decreased from  $117\text{ g}/\text{m}^2$  to  $100\text{ g}/\text{m}^2$  in a surgical aortic valve replacement (SAVR) group and  $114\text{ g}/\text{m}^2$  to  $108\text{ g}/\text{m}^2$  in a TAVI group after 3 months with further reductions at one year. Whether these global changes in LV remodelling translate into improvements in microvascular function, and hence improve the diagnostic accuracy of FFR is not yet known.

If TAVI/SAVR results in a significant improvement in LV remodelling and microvascular function, it should be expected that the current invasive gold-standard for measuring microvascular resistance (IMR; index of microcirculatory resistance) would improve several months after the valve intervention. If this is the case then the FFR measurement should be more accurate (as it is in patients without aortic stenosis). The question is whether a pre-TAVI/SAVR index (based on a combination of FFR and IMR) could be used in the future for assessing intermediate lesions in these patients. Developing a “corrected” FFR measurement of intermediate coronary artery lesions based on the presence or absence of microvascular dysfunction would be very useful in the pre-operative work-up of patients with aortic stenosis and would have important prognostic implications. This will be accomplished by first determining the FFR 6 months after intervention (TAVI or SAVR), when it is anticipated that the microvascular function would have returned to normal, and comparing this with the FFR prior to the intervention to determine if there is a significant change in the FFR after intervention. At the same time microvascular function will be assessed in order to develop a “corrected” FFR, which can be used in the future to determine whether or not coronary lesions need to be revascularized in patients with aortic stenosis.

The theoretical model of a serial stenosis by the AS and the coronary narrowing in our study is explained in the figure 1 in the publication of Zelis et al. It is expected that the FFR will indeed decrease after TAVI and that there will be an acute (change of intercept) and chronic (change of slope) effect of the procedure on the coronary resistance. To separate these two issues we will try to measure the FFR immediately after TAVI and 6 months after TAVI. In addition the left ventricular filling pressure/ end-diastolic pressure (LVEDP) will be measured during the TAVI procedure immediately before and after valve implantation. The measurement (the delta LVEDP) will be an important marker of the “intercept” that changes acutely. To make sure the measurements of IMR, FFR and RFR are correct these will be performed twice and an average value will be used. This will also allow us to test the reproducibility.

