## PROTOCOL SUMMARY

Aortic stenosis (AS) is the most common primary valve disease leading to surgery or catheter intervention in Europe, with a growing prevalence due to the aging population. Severe AS is associated with significant morbidity and mortality and is treated by surgical valve replacement (SAVR) or transcatheter aortic valve implantation (TAVI). However, significant coronary artery disease (CAD) is reported in more than 60% of patients with AS, and this concomitant CAD needs to be correctly assessed because untreated significant CAD is associated with adverse outcomes. Current guidelines recommend intra-coronary pressure measurement using either fractional flow reserve (FFR) or non-hyperemic pressure ratios (NHPR) for the assessment of intermediate coronary artery lesions before revascularization. However, correctly identifying hemodynamically significant coronary stenoses by FFR or NHPR is difficult in patients with AS because of the hypertrophic remodeling related to the valve pathology, which interferes with coronary blood flow in the microcirculation and reduces the accuracy of FFR and NHPR. This has resulted in substantial controversy in this field of coronary artery disease and there is currently no clear guideline for the management of AS patients with concomitant CAD. Recent technological advances now permit the concomitant evaluation of FFR/NHPR and microcirculatory function at the time of cardiac catheterization. Using this technology, we will simultaneously evaluate the hemodynamic significance of coronary stenoses (using FFR and a NHPR - Resting Full cycle Ratio [RFR]) and the microcirculatory function (Index of Microcirculatory Resistance, IMR) in patients with AS and CAD prior to SAVR/TAVI. One hundred patients with AS and intermediate CAD will be included in the study. Of them Eighty will undergo AVR and at least 58 will undergo the follow-up at 6 Months. During routine pre-valve replacement cardiac catheterization, measurement of intermediate CAD lesions (by FFR and RFR) and IMR will be performed in duplicate using new software. These measures of CAD severity will be compared with a gold standard non-invasive test (single photon emission computed tomography [SPECT]). This will validate the use of RFR and determine if IMR can be used to improve the ischemia prediction of FFR. In addition, the patients undergoing TAVI the LVEDP will be measured immediately before and after valve implantation and FFR, RFR and IMR will be measured after valve implantation. Subsequently, when these patients undergo a post-intervention (whether SAVR or TAVI) evaluation 6 months after valve replacement, the effect of valve replacement on FFR, RFR and IMR (again in duplicate) will be determined. This will be the first study measuring these parameters before and 6 months after valve replacement. The data will be used to calculate a 'corrected' FFR (or RFR) based on microcirculatory function in these patients, which can then be used in the future to correctly evaluate CAD pre-intervention in patients with AS. This will translate into more efficient management of patients with AS. Fewer of these patients will unnecessarily undergo coronary artery bypass grafting or stenting when the CAD does not need to be treated and, conversely, in those who do require treatment of the CAD, revascularization can be carried out during a single surgery/intervention, avoiding multiple high risk procedures in patients who are already at high peri-operative/peri-interventional risk.

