### Secondary outcomes

2. Measurement of IMR in patients with AS prior to intervention and 6 months after SAVR/TAVI.
  - a. Description of the range of IMR values in a cohort of patients with severe AS.
    - i. Do all patients with severe AS have high microvascular resistance as assessed by IMR?
    - ii. Does IMR change significantly 6 months after TAVI/SAVR? If there is a significant decrease in IMR then this indicates that microcirculatory function improves 6 months after aortic valve intervention.
3. Null hypothesis: the “corrected” FFR (at baseline; based on baseline IMR) does not correlate with the post-intervention FFR.
  - a. If the null hypothesis is upheld then a correction of FFR using baseline IMR does not improve the validity of FFR in patients with severe AS.
4. Null hypothesis: using IMR at baseline does not improve the ischemia prediction of FFR. Ischemia is measured by SPECT (Figure 2).
  - a. If the null hypothesis is upheld then IMR does not improve stratification of coronary ischemia based on FFR.

- b. If a significant proportion of patients with SPECT ischemia have a raised IMR this would support the hypothesis that IMR can be used to correct falsely high (negative) FFR measurements.
- 5. Comparison of the diagnostic performance of FFR and RFR with SPECT ischemia (and compare with findings of Yamanaka *et al*).
- 6. Reproducibility of the FFR, RFR and IMR

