#### 3.3 Patient population

Patients undergoing routine cardiac catheterization during preparation for TAVI or SAVR, who are found to have coronary artery disease, will be approached to take part. A transthoracic echocardiography (TTE) will take place at baseline and at 6 months. A TTE is part of the routine care and almost without risk. The TTE will assess systolic function, diastolic function, right and left ventricular function, valvular function, fluid status, pulmonary pressures and shear wave analysis to assess the stiffness of the heart. These two extra TTE's will be necessary to standardize the assessment of the valve pathology, to ensure our patients are good candidates and to assess the status post intervention in comparison to before the valve procedure. Cardiac catheterization is routinely performed in these patients and intra-coronary hemodynamic measurements are routinely used during the assessment of coronary artery disease. SPECT is used to confirm the presence of ischemia. Baseline measurements of coronary artery disease and coronary microvascular function (IMR) will be carried out during the baseline cardiac catheterization if intermediate coronary artery lesions (defined as a coronary artery stenosis in the proximal part of a major coronary artery of 50-90% stenosis). During the six-month cardiac catheterization the coronary artery disease is assessed. During this procedure an additional measure of microvascular function (IMR) will be performed. FFR is routine clinical practice, but the additional measurement of IMR will be investigatory.

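### The corrected FFR uses baseline FFR and IMR only, although the plan expects valve relief itself to change FFR; valve severity should enter the model, and IMR should be judged by what it adds

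*Combined protocol and SAP*

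**What the plan says.** - **Ingredients of the correction.** The Background proposes a "pre-TAVI/SAVR index (based on a combination of FFR and IMR") and speaks of a corrected "measurement of intermediate coronary artery lesions based on the presence or absence of microvascular dysfunction". The Synopsis lists as a secondary endpoint "Corrected FFR (based on baseline IMR) correlates with the post-intervention FFR". The Protocol Summary says the correction is "based on microcirculatory function in these patients, which can then be used in the future to correctly evaluate CAD pre-intervention". None of these places names a valve or loading term.
- **Expected mechanism.** The Background adopts a serial-stenosis model and states that "there will be an acute (change of intercept) and chronic (change of slope) effect of the procedure on the coronary resistance". Delta LVEDP is named as a marker of the acute part, and FFR immediately after TAVI is meant to separate the two parts. Sections 3.8 and 4 schedule these measurements at the time of TAVI.
- **Test.** Under Study objectives, Secondary outcomes, item 3, the null hypothesis is that the corrected FFR "does not correlate with the post-intervention FFR".
- **Analysis.** Section 9.2 compares baseline with 6 months. It gives no formula for the corrected FFR and uses neither the immediate post-TAVI values nor delta LVEDP.
- **Valve data.** Section 3.3 plans echocardiography at baseline and 6 months: "The TTE will assess systolic function, diastolic function, right and left ventricular function, valvular function" are among the items assessed.

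**The concern.** The corrected FFR has to predict the 6-month FFR. On the plan's own model that target contains an acute part from relieving the valve and a chronic part, but the correcting factor addresses only the microcirculation.

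Two things can follow if the acute part differs between patients according to valve severity. Where IMR is unrelated to severity, the correction omits a source of variation and predicts less precisely. Where IMR is related to severity, IMR picks up part of the valve effect, which is then read as microvascular. The Background makes some relation plausible, since it links aortic stenosis to increased left ventricular mass and microvascular dysfunction.

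Attribution matters because the corrected FFR is intended for future pre-operative use. The Expected outcomes text, under the SPECT objective, also foresees reading FFR together with microvascular resistance in other patient groups. An apparent IMR effect that came from the aortic valve need not carry over to them.

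**Working it through.** **1. The plan's own figure.** Section 9.1 gives 58 pairs for a fall from 0.82 to 0.79, SD 0.08, alpha 0.05, power 0.80. Taking 0.08 as the SD of the within-patient change, two-sided, the normal approximation is (1.96 + 0.842)² × (0.08/0.03)² = 7.85 × 7.11 = 55.8, so 56. The exact paired t-test has 79.5% power at 57 and 80.2% at 58. The figure reproduces and is not in dispute. No sample size is given for the corrected-FFR objective, so 58 is used below.

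**2. What the stated correlation test can show.** Assume baseline and 6-month FFR each have SD 0.08 and the change also has SD 0.08. Then 0.08² = 2 × 0.08² × (1 − r), so r = 0.5 between baseline and 6-month FFR. By Fisher's transformation, atanh(0.5) × √55 = 0.549 × 7.416 = 4.07, and power is Φ(4.07 − 1.96) = 98%. Baseline FFR with no correction at all would therefore reject the null of no correlation in about 98% of trials. Correlation is also unchanged when a constant is subtracted, so it cannot detect a systematic shift.

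**3. Credit given to IMR when the valve term is absent.** Assumptions, none of which the documents give: valve severity explains a share b² of the variance of the FFR change, IMR correlates ρ with severity, and IMR has no effect of its own. IMR then correlates ρb with the change (sign aside). With m = atanh(ρb) × √55, the chance that the IMR coefficient is significant at 0.05 is Φ(m − 1.96) + Φ(−m − 1.96). The result does not depend on the SD.

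| ρ | 9% explained (b = 0.3) | 25% explained (b = 0.5) |
|---|---|---|
| 0 | 5% | 5% |
| 0.1 | ρb 0.03, m 0.22: 5.6% | ρb 0.05, m 0.37: 6.6% |
| 0.2 | ρb 0.06, m 0.45: 7.3% | ρb 0.10, m 0.74: 11.5% |
| 0.3 | ρb 0.09, m 0.67: 10% | ρb 0.15, m 1.12: 20% |
| 0.5 | ρb 0.15, m 1.12: 20% | ρb 0.25, m 1.89: 47% |

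Simulated trials agree within about two percentage points (5–6%, 7–11%, 10–19% and 18–48% for the four non-zero correlations). Regressing 6-month FFR on baseline FFR and IMR gives nearly the same rates as regressing the change. With the severity variable in the model, the rate returns to about 5%.

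**4. Precision lost when ρ = 0.** There is no false credit, but including severity would lower the residual SD from 0.080 to 0.08 × √0.75 = 0.069 (25% explained) or 0.08 × √0.91 = 0.076 (9% explained).

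**5. Uniform shift.** If every patient's FFR fell acutely by the same amount, a fitted intercept would absorb it and the IMR coefficient would be unbiased.

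**6. Gradient as a proxy.** Take ρ = 0.5 and 25% explained by the true acute driver, and let gradient correlate 0.7 with that driver. The partial correlation of IMR with the change, given gradient, is (0.25 − 0.35²)/(1 − 0.35²) = 0.145. Then m = atanh(0.145) × √54 = 1.08 and the rejection rate is 19%. If gradient correlates only 0.5 with the driver, the partial correlation is (0.25 − 0.25²)/(1 − 0.25²) = 0.20, m = 1.49 and the rate is 32%. Adjustment reduces the false credit from 47% but does not remove it.

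**The case against.** The other side has several good points.

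- **The rates do not belong to a planned test.** A reader might infer that the study has a false-positive rate of up to 47%. The documents do not support this: they specify a correlation between corrected and 6-month FFR, and no test of an IMR coefficient. The rates show what could happen once a model is fitted. This stands, although the planned correlation test is itself uninformative about IMR (step 2).
- **Prediction is not attribution.** If IMR tracks severity, it can legitimately help to predict 6-month FFR. The two harms trade off: the more of the valve effect IMR carries, the less the correction misses. This stands. Misattribution affects the microvascular interpretation and its transfer to other patients.
- **The acute effect is described as a change of intercept.** If uniform, it does no harm. The documents do not say that it varies with gradient, and restricting entry to severe stenosis narrows the range of severity. This stands, and it is why low correlations belong in the table.
- **The plan does not ignore the acute effect.** A reader might infer that it does, but FFR, RFR and IMR immediately after TAVI and delta LVEDP are scheduled to separate it. They cannot fill the gap in the formula: they exist only in TAVI patients, are known too late for a pre-intervention index, and do not reach section 9.2.
- **The presence-or-absence wording is not an analysis rule.** A reader might infer that IMR will be dichotomised. No cut-off is given, and the Synopsis and objectives refer simply to baseline IMR. The wording needs aligning, nothing more.

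**Conclusion.** The concern holds in a limited form. The plan expects an acute effect of valve relief on FFR but builds its correction from baseline FFR and microvascular function only, and section 9.2 supplies no model that would bring in the valve. The consequence depends on two unknowns: whether the acute change varies with valve severity, and how closely baseline IMR follows severity. Over the assumed range the effect runs from negligible (6–7% rejection against a nominal 5% at a correlation of 0.1) to serious (20–47% at 0.5), and it is nil for a uniform shift. The documents do not settle where the truth lies.

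The weakness of the criterion for success is firmer. On the planning SDs as read in step 2, baseline FFR alone would pass the correlation test in about 98% of trials, so passing says little about IMR. The point concerns a secondary objective, and the primary comparison of FFR before and 6 months after intervention is unaffected. It should still be settled before analysis, because the corrected FFR is the tool the study intends to deliver.

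**What to change.** 1. In section 9.2, define the corrected FFR as the prediction from a regression of 6-month FFR on baseline FFR, baseline IMR (continuous, log scale if skewed) and baseline valve severity. Name one severity measure in advance, either mean gradient or valve area from the baseline echocardiogram.
2. Judge IMR by its added contribution over baseline FFR plus valve severity: its coefficient with confidence interval and the reduction in residual SD. Reword Secondary outcomes item 3 to match, in place of a null of no correlation.
3. State that gradient is an imperfect proxy for the acute effect, so any remaining IMR effect is to be interpreted with caution.
4. Add a supporting analysis in TAVI patients that uses the immediate post-TAVI FFR and delta LVEDP to split the change into acute and chronic parts, and relate baseline IMR to each part.
5. In the Background, replace the presence-or-absence wording by baseline IMR, in line with the Synopsis and objectives.

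The cost is SAP and protocol wording, one extra degree of freedom out of about 58 observations, and a slightly more complex formula. Baseline echocardiography already assesses the valve, and the TAVI measurements are already scheduled, so no procedure is added. It should be confirmed that the chosen severity measure is recorded on the case report form.
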